#### **Primary objective endpoints:**

Efficacy:

- ORR at days 35 and 77 in subjects receiving pembrolizumab monotherapy
- ORR at day 77 in subjects receiving pembrolizumab  $\pm$  standard induction chemotherapy
- Clinical Benefit Rate (CBR) at days 35 and 77 in subjects receiving pembrolizumab monotherapy

Safety:

- Incidence and severity of GvHD after administration of pembrolizumab
- Grade 3-5 Regimen-related toxicities (RRT) per CTCAE v4
- Incidence of immune mediated toxicities attributable to pembrolizumab

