#### 5.2.1.2 Dose Modification (Escalation/Titration/Other)

After initiated study treatment, the use of chemotherapy prior to day 35 bone marrow biopsy (or two cycles of pembrolizumab) is discouraged.

- Systemic Chemotherapy may be instituted in the following scenarios:

- Evidence for progressive AML or MDS on day 35 bone marrow biopsy. Progression will be defined as a minimum of > 5% increase in the absolute marrow blasts from pre-treatment biopsy. For example, increase in bone marrow blast from 10% on pretreatment biopsy to 25% on day 35 marrow examination OR

- At the discretion of the treating physician for impending rapidly progressive relapse (e.g. rapid increase in peripheral blast % or hematologic instability. These situations should be discussed in consultation with the study PIs OR
- Alternatively, subjects with minimal progression may remain on monotherapy if deemed there may be potential for subsequent clinical response or deemed poor candidates for systemic chemotherapy. For example, a subject who is tolerating pembrolizumab at day 35 of treatment with increase in bone marrow blasts to 15% at day 35 from 9% at pre-treatment will be recorded as progression but may remain on monotherapy to complete four dose of induction (phase I) at investigator's discretion.

- The chemotherapy regimen will be at the discretion of the treating physician and may include hypomethylation therapy or cytotoxic chemotherapy including high dose ara-C (e.g. FLAG) and/or anthracycline-based regimens. Other investigational agents are not permitted or the subject will be removed from further pembrolizumab and placed into follow-up.

Adverse events (both non-serious and serious) associated with pembrolizumab exposure may represent an immunologic etiology. These adverse events may occur shortly after the first dose or several weeks after the last dose of treatment. Pembrolizumab must be withheld for drug-related toxicities and severe or life-threatening adverse events (AEs) as per Table 3 below. Pembrolizumab must also be permanently discontinued in patients who develop  $\geq$  Grade 3 acute GvHD requiring systemic corticosteroids. Pembrolizumab should be temporarily held if acute GVHD grade II occurs. Pembrolizumab may be re-initiated once acute GVHD improves to < grade II. See Section 5.4 for supportive care guidelines, including use of corticosteroids.

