#### **5.6 Subject Withdrawal/Discontinuation Criteria**

Subjects may withdraw consent at any time for any reason or be dropped from the trial at the discretion of the investigator should any untoward effect occur. In addition, a subject may be withdrawn by the investigator or the Sponsor if enrollment into the trial is inappropriate, the trial plan is violated, or for administrative and/or other safety reasons. Specific details regarding discontinuation or withdrawal are provided in Section 7.1.4 – Other Procedures.

A subject must be discontinued from the trial for any of the following reasons:

- The subject or legal representative (such as a parent or legal guardian) withdraws consent.
- Unacceptable adverse experiences as described in Section 5.2.1.2
- Intercurrent illness that prevents further administration of treatment
- Investigator's decision to withdraw the subject
- The subject has a confirmed positive serum pregnancy test
- Noncompliance with trial treatment or procedure requirements
- The subject is lost to follow-up
- Administrative reasons

The End of Treatment and Follow-up visit procedures are listed in Section 6 (Protocol Flow Chart) and Section 7.1.5 (Visit Requirements). After the end of treatment, each subject will be followed for 30 days for adverse event monitoring (serious adverse events will be collected for 90 days after the end of treatment as described in Section 7.2.3.1). Subjects who discontinue for reasons other than progressive disease will have post-treatment follow-up for disease status until disease progression, initiating a non-study cancer treatment, withdrawing consent or becoming lost to follow-up. After documented disease progression each subject will be followed by telephone for overall survival until death, withdrawal of consent, or the end of the study, whichever occurs first.

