## 6.0 TRIAL FLOW CHART

Study Period:	Screening Phase		Treatment Cycles Phase I: Induction				Response Post- Induction	Treatment Cycles Phase II: Maintenance	Response Post- Maintenance	Post-Treatment	
Treatment Dose/Title Day (D)	Pre- screening	Main Study Screening	1 (D1)	2 (D22)	3 (D43)	4 (D64)	(D77)	Doses 5 – 17 (D85 - D365)*	End of Treatment (D365)	Follow-up: 30 and 90 Days After Treatment up to D455†	Relapse‡
Scheduling Window (Days):	Days -21 to -1	Days -21 to -1	± 3	± 3	± 3	± 3	±7	± 3	± 14	± 14	n/a
Administrative Procedures											
Informed Consent		X									
Inclusion/Exclusion Criteria	X	X									
Subject Identification Card		X									
Demographics and Medical History		X									
Prior and Concomitant Medication Review		X					X				
Study Treatment Administration			X	X	X	X		X			
Post-study Therapy Response Status									X		
Survival Status									X		X
Clinical Procedures/Assessments											
Review Adverse Events		X	X	X	X	X	X	X	X	X	
Full Physical Examination		X	X	X	X	X	X				
Directed Physical Examination								X	X	X	
Vital Signs and Weight		X	X	X	X	X	X	X	X	X	
ECOG OR Karnofsky Performance Status		X	X	X	X	X	X	X			
Laboratory Procedures/Assessments: analysis performed by LOCAL laboratory											
Pregnancy Test – Urine or Serum b-HCG		X	X	X	X	X	X				
PT/INR and aPTT		X	X	X	X	X					
CBC with Differential		X	X	X	X	X	X	X	X	X	
Comprehensive Serum Chemistry Panel		X	X	X	X	X	X	X	X	X	
LDH and Uric acid		X	X	X	X	X					
Urinalysis		X	X	X	X	X		X			

Study Period:	Screening Phase		Treatment Cycles Phase I: Induction				Response Post- Induction	Treatment Cycles Phase II: Maintenance		Response Post- Maintenance	Post-Treatment	
Treatment Dose/Title Day (D)	Pre- screening	Main Study Screening	1 (D1)	2 (D22)	3 (D43)	4 (D64)	(D77)	Doses 5 – 17 (D85 - D365)*		End of Treatment (D365)	Follow-up: 30 and 90 Days After Treatment up to D455†	Relapse‡
Scheduling Window (Days):	Days -21 to -1	Days -21 to -1	± 3	± 3	± 3	± 3	±7	± 3		± 14	± 14	n/a
T3, FT4 and TSH		X	X	X	X	X		X				
Efficacy Measurements												
Bone Marrow Morphology§				D35 (±5)			X			X		X
Bone Marrow Flow Cytometry§				D35 (±5)			X			X		X
Bone Marrow Cytogenetics§				D35 (±5)			X			X		X
Tumor Biopsies/Archival Tissue Collection/Correlative Studies Blood												
Pre-transplant Bone Marrow Biopsy Specimen Collection		X										
Correlative Studies: Bone Marrow Aspirate§		X		D35 (±5)			X			X		X

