Correlative Studies: Blood Collection§, ¶		X	D14 (+5)	D35 (±5)	D56 (±5)		X	D168 (±7) D252 (±7)		X	D425 (±14)†	X
Correlative Studies: Buccal Swabs		X										
Chimerism Analysis (VNTR) (Peripheral Blood)**		X		X			X			X		X

\*Phase II Maintenance treatment: For subjects achieving CR / PR as determined by day 77 response post-induction without significant pembrolizumab related toxicity. Subjects without CR / PR at day 77, relapse / progression after day 77 or clinically significant toxicity during the treatment will be considered off treatment and will be placed into follow-up.

†Follow up: Toxicity assessments will be for 30 days after last dose of pembrolizumab. Longer follow-up for up to 90 days, if applicable, based on continuing SAE / AE that was observed in the treatment period or an events of clinical interest (ECI). Follow up for survival will be up to 90 days after pembrolizumab or D455 (±14) for subjects completing

maintenance and a research blood collection will be obtained. Subjects not initiating or completing maintenance will complete 30 day toxicity assessments and then be followed only for survival (through D365 after initiating pembrolizumab). Subjects in CR/PR not completing maintenance for toxicity may have additional research specimens collected per investigators discretion (see below note). ‡ Relapse denotes collection of unplanned / unscheduled bone marrow aspirate, biopsy and correlative studies at time of clinical suspicion of relapse (if CR) or progression of malignancy at any time during treatment and follow-up periods.

§Bone marrow morphology based on aspirate and/or core biopsy, flow cytometry and  $\pm$  cytogenetics will be performed on day 35 (+5) after dose #2, day 77 ( $\pm$ 7) after dose #4, day 365 ( $\pm$ 14) after completing maintenance. An end of treatment bone marrow may be performed prior to day 365 in subjects in CR/PR who do not complete full maintenance therapy due to toxicity. Subjects removed from further treatment due to documented relapse are not required to undergo further bone marrow studies for research purposes. Cytogenetic analysis may be omitted if there are not pre-treatment cytogenetic anomalies of clinical interest.

||Comprehensive Serum Chemistry Panel should include Magnesium and Phosphorus.

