### **7.1.1.6 Assignment of Screening Number**

**A screening number will be assigned to all subjected being screened.**

## **7.1.2 Clinical Procedures/Assessments**

### **7.1.2.1 Adverse Event (AE) Monitoring**

The investigator or qualified designee will assess each subject to evaluate for potential new or worsening AEs as specified in the Trial Flow Chart and more frequently if clinically indicated. Adverse experiences will be graded and recorded throughout the study treatment and during the safety follow-up period (30 days after the last dose of pembrolizumab) according to NCI CTCAE Version 4.0 (see Section 11.3). Adverse events in the post-treatment follow up period will not be recorded or reported unless they represent continuing adverse events from the treatment period related to pembrolizumab therapy.

Toxicities will be characterized in terms regarding seriousness, causality, toxicity grading, and action taken with regard to trial treatment.

For subjects receiving treatment with pembrolizumab all AEs of unknown etiology associated with pembrolizumab exposure should be evaluated to determine if it is possibly an event of clinical interest (ECI) of a potentially immunologic etiology (termed immune-related adverse events, or irAEs); see the separate ECI guidance document in Appendix 4 regarding the identification, evaluation and management of potential irAEs.

Please refer to section 7.2 for detailed information regarding the assessment and recording of AEs.

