##### 7.1.4.3 Treatment Period

**"Treatment Period"** is defined as the first day of pembrolizumab through 30 days after the last dose of pembrolizumab – from 1st to 4th doses (or 17th dose if receiving maintenance). The assessment and reporting period for **adverse events (AE) related to the pembrolizumab** will start from the first pembrolizumab administration until 30 days after the last pembrolizumab administration.

**"Follow-up Period"** is defined as the first day the subject is no longer within the treatment period (e.g. 31 days after last administration of pembrolizumab) until six months after date of initiating study treatment.

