## **8.0 STATISTICAL ANALYSIS PLAN**

### **8.1 Statistical Analysis Plan Summary**

The statistical plan for this feasibility study of pembrolizumab for relapse after HCT is primarily directed toward the primary objective of safety and feasibility after HCT. The trial will additionally estimate the proportion of patients responding to pembrolizumab monotherapy by overall response rate (ORR). The ORR (CR+PR) will also be estimated at day 35 and 77 for subjects receiving  $\geq$  one dose of single agent pembrolizumab. If progression is noted subjects may receive standard induction chemotherapy. Subjects who are administered standard induction chemotherapy prior to day 77 (for any reason) will be considered non-responders for ORR of pembrolizumab monotherapy. However, we will perform a planned subset analysis to determine the ORR at day 77 for subjects receiving pembrolizumab followed by systemic chemotherapy.

The incidence of grade 3-4 acute GvHD and significant ( $\geq$  grade 3) immune mediated toxicities will be estimated at the conclusion of the treatment period which is 30 days after the last dose of pembrolizumab. Overall survival (OS) and Disease Free Survival (DFS) at 12 months will be calculated by Kaplan Meier methods. The observation period for OS and DFS will begin at the confirmed date of relapse after HCT until death or last scheduled clinical follow up. These observations will assist in determining whether further investigations are warranted after HCT.

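### Severe immune-mediated toxicity that starts more than 30 days after the last dose has no defined place in the primary safety estimate, and some of it may not be recorded

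*Combined protocol and SAP*

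**What the plan says.** **Endpoint and analysis.** The primary safety endpoints in 4.2.2.1 include "Incidence of immune mediated toxicities attributable to pembrolizumab". Section 8.2.1 repeats that item with neither a grade nor a window, and its grade 3-5 regimen-related toxicity (RRT) item has no window either. The only stated window is in 8.1: grade 3 or higher "immune mediated toxicities will be estimated at the conclusion of the treatment period which is 30 days after the last dose of pembrolizumab". The same sentence of 8.1 gives grade 3-4 acute GvHD the same time point.

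**GvHD in 8.2.1.** Item (a) counts severe acute GvHD during induction and for 30 days after the last induction infusion. Item (b) counts total GvHD (acute grade 2-4 and new chronic) through 90 days after the last infusion, with censoring of off-study subjects at other immune therapies.

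**Expected timing.** Section 5.2.1.2, on events with a possible immunologic cause: "These adverse events may occur shortly after the first dose or several weeks after the last dose of treatment".

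**Recording.** Under 7.1.4.3 the assessment period for related adverse events "will start from the first pembrolizumab administration until 30 days after the last pembrolizumab administration". Under 7.1.2.1, later adverse events "will not be recorded or reported unless they represent continuing adverse events from the treatment period related to pembrolizumab therapy". The flow chart has a column headed "Follow-up: 30 and 90 Days After Treatment up to D455" with adverse event review marked. Its footnote says that subjects who do not start or complete maintenance "will complete 30 day toxicity assessments and then be followed only for survival".

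**Expedited reporting.** Section 7.2.3.1 requires all SAEs to 30 days after treatment, and related SAEs at any time. Section 7.2.3.2 requires events of clinical interest (ECIs) to 90 days, or to 30 days if new anticancer therapy starts.

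**The concern.** The protocol expects immune-mediated events to appear weeks after dosing stops, but the only dated estimate for them closes at day 30, and routine recording of new events closes with it. For GvHD, which 8.2.4 treats as distinct from immune-mediated toxicity but possibly overlapping with it clinically, the plan adds a count to day 90. For immune-mediated toxicity it does not say what happens to an event on days 31 to 90.

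This is a primary safety endpoint in a trial of 20 subjects, where one subject is 5 percentage points. If late events are left out, the report gives a correct 30-day incidence but understates the toxicity that follows treatment. If they are included on the strength of the open-ended 8.2.1 bullet, they come from a period with incomplete and uneven recording. The choice would be made after the data are seen.

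**Working it through.** The plan gives no figure for this window, so the check is mainly of the text.

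**1. Calendar.** Last dose of k three-weekly doses falls on day 1 + 21(k − 1).
- k = 4: 1 + 63 = D64. The 30-day cut is D94 and the 90-day cut is D154.
- k = 17: 1 + 336 = D337. The 30-day cut is D367 and the 90-day cut is D427.

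D154 lies inside the six-month follow-up period of 7.1.4.3, and D427 lies before the D455 of the flow chart. A subject who stops part-way through maintenance can fall outside the six months: k = 6 gives D106, and 106 + 90 = D196.

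**2. Where an event starting on days 31 to 90 goes.**

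| Event | Recorded? | Place in section 8 |
|---|---|---|
| Grade 3-4 acute GvHD | Needed for 8.2.1(b) | Counted in 8.2.1(b) |
| Immune-mediated, grade 3 or higher, related, serious | Yes, at any time (7.2.3.1) | Outside the 8.1 window; 8.2.1 bullets silent |
| Same, non-serious but an ECI | Yes, to 90 days (7.2.3.2), or 30 if new anticancer therapy starts | As above |
| Same, non-serious and not an ECI | Generally not (7.1.2.1, 7.1.4.3) | As above, and no data to count |

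The second and third rows have data without a defined estimate. The fourth may have neither.

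**3. Size per subject.** 1/20 = 5 percentage points. The documents give no onset times and no expected rate, so the number of late subjects is an assumption: 0, 1 or 2 of 20 gives 0, 5 or 10 points.

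**4. Illustration.** Exact (Clopper-Pearson) two-sided 90% intervals. The method reproduces the plan's own interval in 8.2.2 for 4 of 20, stated as 7% to 40%: the exact result is 7.1% to 40.1%. Suppose 5 of 20 subjects have an event by day 90:
- none late: 5/20 = 25% (10.4% to 45.6%) at day 30;
- one late: 4/20 = 20% (7.1% to 40.1%) at day 30;
- two late: 3/20 = 15% (4.2% to 34.4%) at day 30.

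The intervals overlap widely.

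**5. Why the number observed matters.** With no late event among n subjects still observed, the upper limit of the same 90% interval on the days 31 to 90 risk is 1 − 0.05^(1/n):
- n = 20: 13.9%;
- n = 10: 25.9%;
- n = 5: 45.1%.

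A statement that no late events were seen means little without n.

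**The case against.** The strongest case is that nothing in section 8 excludes late events. The 8.2.1 immune-mediated bullet says what will be estimated with no cut-off, the RRT bullet beside it has none either, and the 30-day sentence sits in a summary section and concerns a severe subset. This stands in part. A reader might infer that the plan shuts late severe immune-mediated events out of every estimate, or that the choice of label settles whether an event counts. The documents do not go that far. They assign late GvHD to a count and leave late immune-mediated events unassigned. That gap still matters, because the open bullet cannot count events that 7.1.2.1 and 7.1.4.3 tell sites not to record.

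Second, the GvHD comparison is not like with like. Item (b) is a broad total-GvHD count; the dedicated severe-GvHD estimates also stop at 30 days, and item (a) covers induction only. This stands. Item (b) shows that the plan regards days 31 to 90 as worth following, but it does not show that 30 days is wrong. A 30-day incidence is a valid estimate of what it names, and it matches the treatment period and routine collection.

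Third, other rules catch late events. Related SAEs are reportable at any time, and many grade 3 events would be serious through hospitalisation. ECIs run to 90 days, and 7.1.2.1 describes immune-related events as ECIs. The list in 7.2.3.2 names only overdose and a hepatic laboratory pattern, but it is not worded as exhaustive, and the guidance that 7.1.2.1 cites is not in the documents. So the unrecorded group may be small. These remain reporting rules, not estimates.

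Finally, a reader might infer from 5.6, where "serious adverse events will be collected for 90 days after the end of treatment as described in Section 7.2.3.1", against the 30 days in that section, that late attributable SAEs are lost. They are not, because the any-time rule for related SAEs covers them. The mismatch matters mainly for unrelated SAEs.

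**Conclusion.** The point holds as a gap in definition and recording. A late attributable grade 3 or higher immune-mediated event has no defined place in the primary safety estimate and, if non-serious and not an ECI, may not be recorded. The documents do not support calling the 30-day estimate wrong or biased for its own target.

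The effect is probably small and its size is unknown: 5 percentage points per subject of 20, with the range of 0 to 2 subjects assumed. The conclusion rests on reading 8.1 as the only stated window and on 7.1.2.1 and 7.1.4.3 being followed as written. No stopping or promising-drug rule is affected. The interim rules count severe acute GvHD, the monitoring window given in 8.2.4 ends 30 days after the last induction dose, and the promising-drug criteria concern clinical benefit and complete remission. This is a cheap improvement, held with medium confidence.

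**What to change.** **Analysis (8.1, 8.2.1).** Keep the 30-day estimate. Give the 8.2.1 immune-mediated bullet a second descriptive count: the number and proportion of treated subjects with a first attributable grade 3 or higher immune-mediated event through 90 days after the last infusion.
- Show days 31 to 90 separately, with the number of subjects still under observation.
- Treat death without the event as a competing event, so that these subjects stay in the denominator.
- End observation at non-protocol anticancer or immune therapy, in line with the censoring in 8.2.1(b).
- Flag events that follow protocol-permitted chemotherapy, where attribution is weaker.

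**Recording (7.1.2.1, 7.1.4.3, flow-chart follow-up footnote).** Require new-onset events of this kind to be recorded to day 90, including in subjects whose 90-day point falls after the six-month follow-up limit in 7.1.4.3.

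**Cost.** Mostly wording. The 30- and 90-day follow-up column already marks adverse event review, directed examination, vital signs, blood count and chemistry, and 8.2.1(b) already needs GvHD followed to day 90. The drawbacks are slightly more recording, less certain attribution of late events, and incomplete ascertainment in subjects followed only for survival, who may be reached only by phone every 12 weeks. Thyroid tests are not marked in the follow-up column, so late thyroid events would depend on clinical detection.

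Reconciling the SAE periods in 5.6 and 7.2.3.1 is separate housekeeping.

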## 3.2 Secondary Objective(s) & Hypothesis(es)

### 3.2.1 Secondary Objectives

- 1) Estimate the one-year overall and disease-free survival in patients administered pembrolizumab for relapse after HCT

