## 4.0 BACKGROUND & RATIONALE

Allogeneic stem cell transplantation provides the only modality with curative potential for many patients with life-limiting hematologic malignancies, particularly those with acute myelogenous leukemia (AML).

**Relapse After Allo-HCT:** According to the Center for International Bone Marrow Transplant Registry (CIBMTR), approximately 40% of mortality after allogeneic hematopoietic cell transplantation (HCT) occurs from relapse. To our knowledge, there have been no successful approaches for reducing relapse after HCT. In AML, relapse rates range from 25% to 65% depending on HCT and disease specific risk factors including conditioning intensity, T cell depletion, cytogenetic profile and status of disease at the

time of HCT. Refractory or relapsed AML, not in remission at time of HCT, has the highest relapse, approximately 60% or greater.

Management of relapse has been unfortunately met with little success and the proportion of patients with long term survival after relapse HCT remains unacceptably low. Although the use of Donor Lymphocyte Infusion (DLI), often in combination with chemotherapy has become a commonly utilized treatment approach, the long term outcomes remain poor and the incidence of Graft vs. Host Disease (GvHD) after DLI is a significant limitation to its overall success. For example, 13% of patients with AML survived one-year if relapse occurred 6 months after HCT (Bejanyan et al. BBMT 2015).

[figure not shown]

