**Secondary objective endpoints:**

- Estimate overall survival (OS) and disease-free survival (DFS) at one year in patients who receive pembrolizumab for relapse after allogeneic HCT.

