#### **5.1.2 Subject Inclusion Criteria**

In order to be eligible for participation in this trial, the subject must:

1. Acute Myeloid Leukemia (AML), Acute Lymphoblastic Leukemia (ALL) or Myelodysplastic Syndrome (MDS) in confirmed relapse based on bone marrow examination after allogeneic HCT. Biopsy confirmed myeloid sarcoma or extramedullary AML may also be considered.
2. Confirmation of 'measurable disease' by blast % will be defined as a marrow blast percentage of > 5% by morphologic assessment on bone marrow examination. This criterion does not apply to myeloid sarcoma, or extramedullary leukemia, which must also show measurable lesion by CT, MRI, PET/CT or photograph (i.e. Leukemia cutis). If marrow blasts of ≤ 5% blasts are enumerated the patient may be eligible only if there is clear (probable or definite) flow cytometric, cytogenetic or molecular aberrations (e.g. FLT3-ITD, NPM1, etc.) documenting relapse of the leukemia associated clone defined prior to HCT.
3. Patient may not have received definitive salvage chemotherapy for their post-transplant relapse within the past 21 days. Use of hydroxyurea is permitted.
4. Be willing and able to provide written informed consent/assent for the trial
5. Be ≥ 18 years of age on day of signing informed consent
6. Be willing to provide tissue from bone marrow biopsies
7. Have a performance status of 0, to 1 on the ECOG Performance Scale. For purposes of HCT, this will correspond to a Karnofsky Performance status of ≥ 80%

8. Demonstrate adequate organ function as defined in Table 1, all screening labs should be performed within 10 days of treatment initiation

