### **5.1.3 Subject Exclusion Criteria**

The subject must be excluded from participating in the trial if the subject:

1. Has had relapse prior to primary neutrophil engraftment or ≤21 days post HCT.
2. Has received >1 line of chemotherapy or other treatment directed towards post-transplant relapse prior to study entry
3. Rapidly progressive relapse requiring urgent chemotherapy as determined by treating physician
4. Is currently participating and receiving study therapy of an investigational agent and received study therapy within 2 weeks of the first dose of treatment. This 2 week washout period would not apply to investigational food ingredients.
5. Has a diagnosis of active GvHD (≥ Grade I). Patients with prior active GvHD that is quiescent (Grade 0) at time of entry may be considered.
6. Receiving systemic steroid therapy of > 10mg prednisone daily or equivalent\*
7. Has received GM-CSF within 14 days of first dose of pembrolizumab
8. Has a known history of active TB (Bacillus Tuberculosis)Hypersensitivity to pembrolizumab or any of its excipients
9. Has had a prior anti-cancer monoclonal antibody (mAb) within 4 weeks prior to study Day 1 or who has not recovered (i.e., ≤ Grade 1 or at baseline) from adverse events due to agents administered more than 4 weeks earlier
10. Has had prior chemotherapy within 21 days, or radiation therapy within 14 days prior to study Day 1 or who has not recovered (i.e., ≤ Grade 1 or at baseline) from adverse events due to a previously administered agent
  - a. Note: Subjects with ≤ Grade 2 neuropathy are an exception to this criterion and may qualify for the study.
  - b. Note: If subject received major surgery, they must have recovered adequately from the toxicity and/or complications from the intervention prior to starting therapy.
11. Has a known additional (secondary) malignancy that is progressing or requires active treatment. Exceptions include basal cell carcinoma of the skin or squamous cell carcinoma of the skin that has undergone potentially curative therapy or in situ cervical cancer.

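### Twelve-month OS is timed from relapse in patients who all had to survive to a first dose, and DFS as written ends where OS ends

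*Combined protocol and SAP*

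**What the plan says.** Section 8.1 plans Kaplan-Meier estimates of OS and DFS at 12 months. On the clock it says "The observation period for OS and DFS will begin at the confirmed date of relapse after HCT", and for both endpoints it ends observation at death or the last scheduled follow-up.

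The population is the treated one. Section 3.2.1: "Estimate the one-year overall and disease-free survival in patients administered pembrolizumab for relapse after HCT". The secondary endpoint list closing Section 4.2.2.1: "Estimate overall survival (OS) and disease-free survival (DFS) at one year in patients who receive pembrolizumab for relapse after allogeneic HCT". Delayed entry, left truncation and landmarking appear nowhere.

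Entry requires disease "in confirmed relapse based on bone marrow examination after allogeneic HCT" (Section 5.1.2; biopsy-confirmed extramedullary disease may also be considered). Treatment can intervene between relapse and entry. Section 5.1.3 excludes only those beyond one line: "Has received >1 line of chemotherapy or other treatment directed towards post-transplant relapse prior to study entry". Both lists impose a washout: "Patient may not have received definitive salvage chemotherapy for their post-transplant relapse within the past 21 days" (5.1.2) and "Has had prior chemotherapy within 21 days, or radiation therapy within 14 days prior to study Day 1" (5.1.3). No maximum interval from relapse to first dose is set.

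Elsewhere the protocol counts from first dose. Section 7.1.3.1.3 makes that day 1, the Section 6.0 footnotes run survival follow-up to D365 from it, and Section 7.1.4.5.1 uses one year from it. Section 7.1.4.3, however, closes the follow-up period six months after treatment starts.

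No section says what counts as a DFS event. Section 8.2.2.1 defines progression for response assessment only. Section 7.1.3.1.3 mentions PFS without defining it.

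**The concern.** A patient who dies after relapse but before a first dose never enters the analysis, while the survival clock of everyone who does enter is already running. Ordinary Kaplan-Meier puts all analysed patients at risk from relapse, so it credits them with an interval in which none of them could have died. That effect can only raise the 12-month figure.

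One-year OS and DFS are the whole of the secondary objective, and Section 8.1 counts them among the observations that will inform whether further study is warranted. An OS figure labelled as measured from relapse is easily set beside published survival after relapse, where early deaths count.

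The DFS problem is separate and needs no assumed numbers. Every subject has active disease at the stated origin and at entry, so being disease-free is not a state that the curve can start from.

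**Working it through.** The plan gives no expected rate, precision or sample-size figure for 12-month OS or DFS, so there is nothing of its own to reproduce.

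**Inputs**
- Number of subjects: 20 (Section 1.0).
- One-year survival: 13%, the only such rate in the documents. Section 4.0 reports that "13% of patients with AML survived one-year if relapse occurred 6 months after HCT". It is AML only, whereas ALL and MDS also enter, so it serves as an illustration.
- Gap L from relapse to first dose: not given. The only documented minimum is about 21 days, for subjects who had chemotherapy for the relapse. Gaps of 7, 60 and 90 days are assumptions.
- Hazard shape: not given. Constant (k = 1), falling (k = 0.7) and rising (k = 1.3) Weibull hazards are assumptions.

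**Clock as written.** Let S(t) = exp(−H·(t/365)^k), with H = −ln(0.13) = 2.040. If everyone analysed survived to L, Kaplan-Meier from relapse estimates S(365)/S(L). For k = 1 and L = 21 this is 0.13 × exp(2.040 × 21/365) = 0.146. For L = 90 it is 0.13 × exp(2.040 × 90/365) = 0.215.

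| Gap (days) | k = 1 | k = 0.7 | k = 1.3 |
|---|---|---|---|
| 7 | 13.5% | 14.8% | 13.2% |
| 21 | 14.6% | 17.1% | 13.7% |
| 60 | 18.2% | 23.1% | 15.8% |
| 90 | 21.5% | 28.0% | 18.1% |

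**Against sampling error.** SE = √(0.13 × 0.87/20) = 0.075. Under constant hazard the shift is 1.6/7.5 = 0.2 SE at 21 days and 8.5/7.5 = 1.1 SE at 90 days.

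**Other baselines** (constant hazard, baseline^(1 − weeks/52.18)). A 20% rate becomes 21.9% with a 3-week gap and 29.9% with 13 weeks. A 30% rate becomes 32.2% and 40.5%.

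**Clock from first dose**, S(365+L)/S(L). Under constant hazard this is 13.0% at every gap. For gaps of 21 and 90 days it is 15.8% and 19.9% with k = 0.7, and 11.7% and 9.2% with k = 1.3. It removes the guaranteed time but answers a different question from survival since relapse.

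**Delayed entry from relapse.** This was simulated in 8,000 trials of 20 subjects, with gaps uniform on 7 to 90 days and constant hazard. The mean estimate was 13.9%, against 17.2% for the clock as written. The target is survival given being alive at the expected earliest entry, day 7 + 83/21 ≈ 11: 0.13 × exp(2.040 × 11/365) = 13.8%. The SD was 8.0 points. The risk set at the first death had median 8 and 5th percentile 2, and in 2.2% of trials the curve reached zero before all subjects had entered.

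**DFS.** Three statements, side by side: the origin is relapse (8.1); all subjects have active disease at that origin and at entry (5.1.2); observation ends at death or last follow-up (8.1). The only event named is death, so the DFS curve is the OS curve.

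**Follow-up.** A six-month end (7.1.4.3) cannot support a 12-month estimate. It also conflicts with the schedule: dose 17 falls on day 1 + 21 × 16 = 337. Sections 6.0 and 7.1.4.5.1 point to D365 or one year.

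**The case against.** The strongest reply is that the conditioning is already stated. Sections 3.2.1 and 4.2.2.1 say that the estimate is for treated patients, and on that footing survival since relapse is a legitimate description of the cohort. The plan sets no OS benchmark or threshold, and Section 8.2.1 calls the analysis descriptive. The only documented minimum gap gives a shift well inside sampling error; the larger shifts rest on assumed gaps and on a 13% rate from a narrower population.

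Most of this stands, and it limits the point to how the figure will be read. It does not remove it: Section 8.1 carries no caveat, the effect runs in one direction however wide the interval, and the gap is uncapped. Nor does it touch DFS.

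Some stronger readings are tempting but unsupported.
- A reader might infer that the trial tests OS against the 13%. That figure is background only.
- A reader might infer that Section 7.1.4.5.1 stops follow-up 90 days after an early last maintenance dose. The Section 6.0 footnotes keep subjects who do not complete maintenance under survival follow-up to D365.
- A reader might infer that replaced subjects are dropped, stretching the guaranteed time to dose 2. Section 5.7 says that they are still monitored for study outcomes.

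**Conclusion.** Both parts hold and should be corrected before analysis. The OS estimate contains guaranteed time and is too high if taken as survival after relapse. The amount cannot be determined from the documents. In the illustration (13% at one year, constant hazard, one common gap, no entry selection) it runs from +0.5 points at 7 days, through +1.6 at 21, to +8.5 at 90, and it is larger if the hazard falls over time. If most subjects are dosed within about three weeks of relapse, the effect is small.

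A reader might go further and conclude that the trial's main inferences are biased. They are not: the promising-drug criteria (8.2.2) and the toxicity stopping rule (8.2.4) do not use OS or DFS. Nor is the OS figure meaningless, provided it is described as conditional on reaching treatment.

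The DFS conclusion rests on the text alone: as written, half of the secondary objective duplicates the other half.

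**What to change.** - **OS.** In Section 8.1, start OS at the first pembrolizumab dose, include every subject with at least one dose, and call it survival from treatment start.
- **Gap.** Report the distribution of the relapse-to-dose interval. If survival from relapse is also reported, use delayed entry at first dose and show the early risk-set sizes. State that selection at entry (performance status, organ function, exclusion of rapidly progressive relapse) remains under any clock.
- **DFS.** Replace it in Section 3.2.1, in the endpoint list of Section 4.2.2.1 and in Section 8.1 with a defined endpoint: either PFS or event-free survival from first dose (progression or death), or relapse-free survival from CR in responders. The first option requires reconciling the progression baselines, which are the pre-treatment biopsy in Section 5.2.1.2 and the prior aspirate in Section 8.2.2.1.
- **Follow-up.** Reconcile the six-month end in Section 7.1.4.3 with the D365 or one-year end in the Section 6.0 footnotes and the survival follow-up section, and obtain vital status at D365 for all treated subjects.

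**Cost.** The OS change is wording plus a vital-status check. The check matters because a relapse clock reaches 12 months before D365, whereas a first-dose clock leaves no margin for subjects who do not complete maintenance. Under the survival follow-up section, contacts are only every 8 weeks, or every 12 weeks where visits are not feasible. At 13% survival about 20 × 0.13 = 2.6 subjects would be alive at D365, so one or two early censorings would matter. OS may look slightly less favourable and will not be directly comparable with from-relapse figures. Delayed entry is unstable with 20 subjects. Replacing DFS means amending the secondary objective and endpoint; PFS may need more disease-status data, while relapse-free survival covers responders only.
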